## Early discontinuation

1. At each research visit, the BISS, and overall clinical impression (CGI-BP) will be completed. Early discontinuation will be defined as any of the following: 1) hospitalization for depression, mania, or suicidality; 2) worsening of depression (CGI-BP change from preceding phase of much or very much worse); 3) treatment emergent mania (BISS mania score >20 and/or CGI-BP change from preceding phase of much or very much worse); 4) Actively suicidal patients as defined by a response score of 3 or 4 on question 4 in the Bipolar Inventory of Symptoms Scale (Thinks of suicide/death several times a day in depth, or has made specific plans, or attempted suicide) OR actively suicidal patients as defined by any of the following responses to questions from the C-SSRS: "Yes" response to questions 4, "Yes" response to question 5, "Yes" response to questions 1, 2 or 3 with scores of 4 or 5 in any of the intensity of ideation items, 5) serious cutaneous adverse reaction meeting at least one of the following criteria: ≥20% body surface involvement, systemic involvement (fever, swollen glands, blood or liver function abnormalities), mucosal or ocular involvement, or hospitalization, 6) intolerable side effects or 7) other administrative criteria as determined by the research team. The dose of lamotrigine or fluoxetine will be discontinued immediately.

2. Special attention will be given to participants who develop suicidal ideation. Participants will be closely monitored at visits and also contacted by telephone to ensure medication compliance and participant safety. The SC will be supervised up by the study psychiatrist and principal investigator and will defer to the physician's judgment as needed. The SC will be trained to notify the RC at the time of the clinical visits or the phone interviews if the subject endorses any suicidal ideation or plans. All questionnaires that involve questions related to depression and/or harm to self or others will be reviewed within 1 working day of receipt from the subject. If a subject endorses suicidality with any of the following: Active suicidal ideation as determined by the investigator. If a subject responds positively to questions regarding the harm of self and/or others, the research team will immediately contact the subject in person or by telephone to discuss their responses. If the subject continues to endorse *suicidal ideation*, the investigator will immediately refer subject to the nearest emergency room and/or psychiatric admission on a voluntary or if need be, involuntary basis. If subject denies suicidal feelings and immediate referral to the emergency room deemed un-necessary, the subject will be recommended to get a referral for appropriate psychiatric consultation from the primary provider. Investigators will notify the primary provider about the need for such referral. If the subject does not have a primary provider, the research consultant will provide a referral for psychiatric consultation. The participant will be asked to provide contact information, including an emergency contact. In an emergency (as determined by the PI) the study team will reach out to the emergency contact if the participant cannot be contacted.

**Remuneration:** Participants will be provided study drugs for free and free parking when they come to any of the study visits or study related procedure.: The participant will be paid \$50.00 at the first visit; last visit: \$50.00.

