**Study Medication**

1. The study PI or Co-I will be in charge of medication administration, dosage and changes at baseline and follow-up visits:
2. Bipolar I, Bipolar II, or schizoaffective disorder depressed
3. Dosing for adults as monotherapy or on lithium or antipsychotic: LTG 25 mg daily x 2 weeks, 50 mg daily x 2 weeks, 100 mg daily x 2 weeks, 200 mg (100 mg bid) x 4 weeks. If patient still has at least mild depressive symptoms (CGI  $\geq$  3) the dose can be increased to 300 mg daily for 2 weeks and 400 mg for 4 weeks. Dose will be held for treatment response and can be reduced for side effect.
4. Fluoxetine dosing: 20mg for month 1, 40mg for month 2, and if still depressed (CGI  $\geq$  3) 60mg for month 3 and 4. Lower doses of fluoxetine will be prescribed for those with side effects. For known 2D6 Poor Metabolizers, fluoxetine will not be dosed > 40mg.
5. Valproate Lamotrigine Titration: 25mg (half tablet) daily for week 1 and week 2, 25mg daily for week 3 and week 4, 50mg daily for week 5-6, 100mg daily for week 7-10, and 100mg daily for week 11-16.

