**Risk mitigation plans:**

As there will be 3 adverse events of special interest for this study (skin rash, antidepressant-induced mania and suicidal ideation), to mitigate those risks there will be a special monitoring and tracking of those events. At each visit, patients will be assessed for treatment-emergent manic symptoms using the BISS scale, for suicidality using the BISS and C-SSRS scales also and all study clinician will assess for skin rash at each visit. In addition, for populations where the risk of antidepressant-induced mania has been shown to be higher than placebo (bipolar I disorder), patients who are randomized to fluoxetine will be required to stay on a mood-stabilizer during the course of the study to decrease the likelihood of a treatment-emergent mania. A Data Safety and Monitoring Board will review safety data every 6 months.

Date and time of last dose of study medication will be gathered at the 1, 2, 4, 8, 12, and 16 week visits. To ensure compliance with the protocol, subject will bring in their medications at each visit for medication counts. The importance of medication compliance will also be discussed with the subject. To study medication compliance and pharmacokinetic pharmacogenomics blood levels of medication will be measured at week 16.

If participants are on current medications and are otherwise candidates for the study, their primary clinician will be contacted as to the relative merits of enrolling in the study. If it is clinically indicated (i.e. medicines are not helping optimally), the subject will be tapered off all psychotropic medications.

2. Adjunctive and concurrent medications. Adjunctive treatments are those used to manage transient associated symptoms (e.g., insomnia) or transient or longer-term medication side effects (e.g., sexual dysfunction). Adjunctive treatments that are not used to treat depression may be taken during the study. However, drugs in the exclusion criteria for this study may not be used as adjunctive therapies. Participants can participate in the study while receiving concurrent medications for general medical conditions as long as there is no contraindication to their use while taking fluoxetine.

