## Management of Serious Adverse Events (SAE)

As mentioned in the prior sections, study participants will be screened for adverse events and serious adverse events by the study team. Regarding SAEs, we will utilize standard FDA classification and forms for SAEs handling and reporting. In general, SAEs will be defined as any event that:

- results in death
- is life threatening
- requires hospitalization (or a prolongation of hospitalization in already hospitalized participants)
- results in a persistent or significant disability or incapacity
- are congenital anomalies or birth defects
- any other adverse event that, based upon appropriate medical judgment, may jeopardize the subject's health and may require medical or surgical intervention.

For the purpose of this study, treatment-emergent mania (as defined previously), treatment-emergent skin rash and treatment-emergent-worsening suicidality (as defined previously) will be treated as SAEs and then will follow the same procedures as any SAE with regards to reporting timelines.

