Based on older guidelines for dosing of lamotrigine, there were some serious side effects, which in clinical trials of bipolar and other mood disorders occurred in approximately 0.08% (0.8 per 1,000) of adults taking lamotrigine as initial monotherapy and 0.13% (1.3 per 1,000) in adults receiving lamotrigine as adjunctive therapy. These side effects can be serious and potentially life-threatening. These are mainly side effects related to the skin, and include Stevens Johnson Syndrome (a severe rash around the eyes, mouth, genital, anal, and other skin areas), toxic epidermal necrolysis (severed blistering and sloughing of the skin), angioedema (swelling under the skin), and hypersensitivity syndrome (an allergy-like reaction with fever, swollen glands, rash, blood or liver problems, and facial swelling). Almost all of the life-threatening rashes have occurred within 2 to 8 weeks after starting to take lamotrigine. However, there have been a few people who developed these rashes months after starting lamotrigine. The only known factor that has been identified to predict the risk of the occurrence or severity of lamotrigine associated rash is age; pediatric participants are at greater risk than adults. Three factors have been suggested as potential causes for an increased risk of serious rash: 1) starting at too high of a dose, 2) increasing the dose too quickly, and 3) coadministration with valproate. The risk is increased to 1 out of every 100 adults who take a combination of lamotrigine and divalproex sodium. In worldwide post-marketing experience, rare cases of rash-related death have been reported, although the numbers are too few to estimate a risk. However, these deaths occurred when using the old dose recommendations. New data would suggest that with more conservative guidelines, as noted in the Physician's Desk Reference and as being followed in this study, this risk is reduced.

Non-serious rashes also occur when taking lamotrigine; however, it is not possible to know which rashes will become severe. Thus any rash, skin discoloration, blister, or mouth sore should be reported immediately. In general, lamotrigine should be discontinued at the first sign of rash, unless the rash is clearly not drug-related. Even if one stops taking lamotrigine, a rash could become severe or permanently disabling or disfiguring. In extremely rare cases, multiorgan failure has been observed in 2

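### The stopping list requires lamotrigine to be stopped only for a serious skin reaction and does not carry over the protocol's own advice to stop in general at the first sign of rash

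*Combined protocol and SAP*

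**What the plan says.** Early discontinuation, item 1, lists seven criteria and orders study drug stopped at once when one is met. Criterion 5 is the only one about skin. It applies to a "serious cutaneous adverse reaction meeting at least one of the following criteria", and the criteria are involvement of at least 20% of body surface, systemic signs, mucosal or ocular involvement, or hospitalization. Criterion 6 is intolerable side effects and criterion 7 is administrative.

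Possible Risks for study medications takes a lower threshold for lamotrigine and gives the reason: "Non-serious rashes also occur when taking lamotrigine; however, it is not possible to know which rashes will become severe". It then advises, as a general rule, that "lamotrigine should be discontinued at the first sign of rash, unless the rash is clearly not drug-related". On timing it says: "Almost all of the life-threatening rashes have occurred within 2 to 8 weeks after starting to take lamotrigine".

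Other sections touch on rash or on side effects:

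- Risk mitigation plans: "all study clinician will assess for skin rash at each visit".
- Management of Serious Adverse Events: "treatment-emergent skin rash and treatment-emergent-worsening suicidality (as defined previously) will be treated as SAEs", with the effect limited to reporting timelines.
- Study Medication, item 3: "Dose will be held for treatment response and can be reduced for side effect".
- Protection Against Risk: participants are told to report rash immediately, and both serious skin reactions (by reference back to the drop-out section) and rashes are monitored.
- Individual Participant Stopping Rules: the investigator may withdraw a participant at any time.

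**The concern.** The section that a site would consult for a stopping decision sets a higher bar than the section that explains the hazard. If an early rash cannot be classified as benign or dangerous, a rule that waits for extensive or systemic involvement waits for the very progression that the risk section says cannot be foreseen. A study physician who works from the Early discontinuation list alone would find no skin criterion met by a limited, possibly drug-related rash, and would find dose reduction offered in Study Medication.

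The main issue is participant safety during titration. A second one is consistency. The trial runs at more than one site, and rash on lamotrigine is an Aim 2 phenotype. If similar rashes lead to a stop in one participant and a lower dose in another, exposure and on-treatment follow-up among the rash cases will depend on who made the decision.

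**Working it through.** The plan states no figure that depends on this point, so the check is mainly a comparison of texts. Take a rash on lamotrigine that is limited, without systemic, mucosal or ocular signs, not leading to hospitalization, and possibly drug-related.

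| Text | What it does for this rash | Stop required? |
|---|---|---|
| Early discontinuation, criterion 5 | Not met | No |
| Early discontinuation, criterion 6 | Met only if judged intolerable; the stop is then mandatory | Only after that judgement |
| Early discontinuation, criterion 7 | Administrative decision by the research team | No |
| Possible Risks for study medications | Advises stopping, as general guidance | Advised, outside the stopping list |
| Study Medication, item 3 | Permits dose reduction; rash not excepted | No |
| Risk mitigation plans | Rash check at each visit | No |
| Management of SAEs | Reported on SAE timelines | No |
| Protection Against Risk | Monitored and reported to the doctor | No |
| Individual Participant Stopping Rules | Investigator may withdraw the participant | No |

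The criteria cannot be read as governing study exit only, with the risk section governing the drug. The Early discontinuation item itself says that the drug is stopped. Protection Against Risk also refers back to that item for serious skin reactions, which supports treating it as the operative rule.

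**Timing.** Without valproate, titration runs "LTG 25 mg daily x 2 weeks, 50 mg daily x 2 weeks, 100 mg daily x 2 weeks" and then 200 mg from week 7. The scheduled increases therefore come at the end of weeks 2, 4 and 6. That is three steps and a rise of 200/25 = 8-fold, all within the 2-to-8-week period in which the protocol places nearly all life-threatening rashes. I leave the valproate schedule out of this count. Its first two entries give 25 mg as half a tablet and then 25 mg, so the starting dose and the first step cannot be read with confidence.

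**Scale only.** Inputs are 200 lamotrigine participants (Participant Population) and rates from Possible Risks for study medications.

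- Stops for rash in premarketing trials, 5%: 200 × 0.05 = 10. The central 95% range of Binomial(200, 0.05) is 4 to 16.
- Serious, mainly skin-related reactions, 0.08% (monotherapy) to 0.13% (adjunctive): 200 × 0.0008 = 0.16 and 200 × 0.0013 = 0.26.
- Risk with divalproex, 1 in 100: 200 × 0.01 = 2, if every participant took the combination.

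These rates come from different sources. The protocol ties the serious rates to older dosing and says that risk is lower under the dosing used here, and their definition need not match criterion 5. They suggest that most rash decisions would fall below criterion 5, but they do not measure how many.

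**The case against.** The strongest reply is that nothing here conflicts. The Early discontinuation list does not say that it is exhaustive, and it does not say to continue below criterion 5. The risk section belongs to the same protocol, so a clinician who stops at the first suspicious rash complies with both. This stands. A reader might infer that the protocol contradicts itself, or that it tells sites to treat through a rash. The documents support neither reading.

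There are also real safeguards. Criterion 6 is mandatory once a side effect is judged intolerable, and the risk section can inform that judgement. Dosing is in the hands of the principal investigator or a co-investigator. Side effects are reviewed weekly under Study Coordination. Any treatment-emergent rash is handled as an SAE, and external sites report SAEs to the lead investigator. These make a bad outcome less likely and limit variation between sites. They give partial cover, because each one monitors, reports or leaves the decision to judgement. A mild rash need not be intolerable to anyone.

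It is also tempting to argue that the other two adverse events of special interest, mania and suicidality, are treated better because they have scored criteria. That argument is weak. Their thresholds are also high, milder forms also meet no scored criterion, and criterion 5 is itself explicit and checkable. I do not rely on it.

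Finally, the advice to stop is worded as general guidance, with an exception for rash clearly not caused by the drug. Any amendment that makes it a rule should keep that exception.

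**Conclusion.** The point holds as an unresolved gap. The operative list requires a stop for a skin event only once it is serious, while the protocol's own safety reasoning supports stopping lamotrigine earlier. No rule requires that earlier stop, and the dose-reduction sentence leaves another course open. This should be corrected, because the stated threshold is the less protective of the two and the correction is small.

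Its size in participants is unknown. A reader might take the figure of about 10 of 200 as the number who would be left on lamotrigine with a rash, or as the number of extra stops that the fix would cause. It is neither. It counts people who were stopped for rash in other trials, and the documents give no incidence of rash of any severity. The conclusion rests on reading Early discontinuation as the operative stopping rule, which its order to stop the drug and the reference back from Protection Against Risk both support.

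**What to change.** One amendment, with wording in two sections.

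1. Early discontinuation, item 1, criterion 5: *On lamotrigine, any rash, unless the study physician documents that it is clearly not drug-related; on either drug, a serious cutaneous adverse reaction [existing list].* The immediate stop already ordered in that item then applies. The two-week taper described in the risk section already gives way to safety concerns, so no separate taper sentence is needed.
2. Study Medication, item 3, repeated at item 5 so that the valproate titration is covered: *Dose reduction for side effects does not apply to such a rash; see Early discontinuation.*

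An optional addition is to hold the next scheduled dose step while a rash is being assessed. No current text provides for this, so it is a new safeguard that goes beyond aligning the two sections.

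The cost is that some participants whose rash would have stayed benign stop lamotrigine before week 16, and their on-treatment response and drug level at that visit are lost. The number cannot be estimated from the documents. Some of them would be stopped anyway by a clinician who follows the risk section. The rash would still be available as the Aim 2 phenotype, and Stopping Rules for Efficacy and Safety already provides for monitoring after study drug is discontinued.

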out of 3,796 participants. In clinical trials with bipolar disorder participants, 2 participants experienced seizures shortly after abrupt withdrawal of lamotrigine. Though there were confounding factors that may have contributed to the occurrence of those seizures, it is important that lamotrigine should not be abruptly discontinued. Unless safety concerns warrant otherwise, the dose of lamotrigine should be tapered over at least a period of 2 weeks. Overdoses of up to 15 g have been reported, some of which were fatal. Overdose can result in ataxia, nystagmus, increased seizures, decreased consciousness level, coma, and intraventricular conduction delay. A recent findings based on FDA's review of adverse event reports submitted to the agency from December 1994 (when the drug was approved) through November 2009 indicate that Lamictal may pose a rare but increased risk associated with aseptic meningitis. A total of 40 cases of aseptic meningitis occurring in pediatric and adult participants taking lamotrigine were identified. The symptoms present in these cases included headache, fever, nausea, vomiting, nuchal rigidity, rash, photophobia and myalgias. These symptoms occurred 1 to 42 days after starting Lamictal. There was one reported death, although the death was not thought to be the result of aseptic meningitis. In most cases, symptoms resolved after lamotrigine was discontinued. Fifteen of these cases reported a rapid return of symptoms following re-initiation of Lamictal; symptoms recurred within 30 minutes to 24 hours following re-initiation of lamotrigine. Symptoms were frequently more severe after re-exposure. Although this is currently not a black box warning, this new rare but serious side effect will be included on an updated black box warning insert for lamotrigine. The research data for this study will be shared as part of the NIH Data Share policy. All participants will be identified by a unique enrollment identification number that will maintain their anonymity. All shared data will be coded by this I.D. All personal information will be kept separate and locked in a file only accessible by the Principal Investigators.

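### Early discontinuation stops lamotrigine immediately even for administrative reasons, against the protocol's own rule to taper over at least 2 weeks unless safety requires otherwise

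*Combined protocol and SAP*

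**What the plan says.** Early discontinuation, item 1, defines early discontinuation by any one of seven criteria:

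1. hospitalization for depression, mania or suicidality
2. "worsening of depression (CGI-BP change from preceding phase of much or very much worse")
3. treatment-emergent mania
4. active suicidality
5. serious cutaneous reaction
6. intolerable side effects
7. "other administrative criteria as determined by the research team"

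The item ends: "The dose of lamotrigine or fluoxetine will be discontinued immediately". That sentence has no exception, no taper and no cross-reference.

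Possible Risks for study medications reports that in bipolar trials "2 participants experienced seizures shortly after abrupt withdrawal of lamotrigine", notes that confounding factors may have contributed, and concludes that "it is important that lamotrigine should not be abruptly discontinued". It then sets the rule: "Unless safety concerns warrant otherwise, the dose of lamotrigine should be tapered over at least a period of 2 weeks". The same section supports stopping lamotrigine when a rash first appears, unless the rash is plainly not due to the drug.

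**The concern.** Two parts of one protocol tell the site to do different things with the same drug. Early discontinuation is where staff will look when they withdraw a participant, and it uses mandatory language. The taper rule stands in the risk text and is worded as what should happen.

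If a lamotrigine participant is withdrawn for a reason unrelated to safety, following the operational section means breaking the safety rule. At stake is avoidable abrupt withdrawal of an anticonvulsant, which the protocol itself links to seizures. This is a question of participant safety and internal consistency. It does not bear on the endpoints, the analysis or the power statement.

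**Working it through.** The plan states no figure on this point, so the check is a comparison of texts, followed by the dose arithmetic.

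**Step 1: each trigger against the safety exception in the taper rule.**

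| Criterion | Does the exception plausibly apply? |
|---|---|
| 5, serious cutaneous reaction | Yes; the risk section itself supports a prompt stop for rash |
| 1, hospitalization; 3, mania; 4, suicidality; 6, intolerable side effects | Reasonably, on clinical judgement |
| 2, worsening depression alone | Arguable; worse depression does not by itself make an abrupt lamotrigine stop safer, but a physician could see a safety concern |
| 7, administrative | Not in general; no safety concern need be present |

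This sorting is a clinical reading. The documents do not classify the triggers. The SAE section says that "treatment-emergent skin rash and treatment-emergent-worsening suicidality (as defined previously) will be treated as SAEs", but that governs definitions and reporting timelines. It does not say when an abrupt lamotrigine stop is justified, so it cannot be used to clear triggers.

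**Step 2: the dose from which an abrupt stop could occur.** Adding up the durations in Study Medication, items 3 and 5:

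| Weeks | Without valproate | With valproate |
|---|---|---|
| 1–2 | 25 mg | half of a 25 mg tablet |
| 3–4 | 50 mg | 25 mg |
| 5–6 | 100 mg | 50 mg |
| 7–10 | 200 mg | 100 mg |
| 11–12 | 300 mg if CGI is 3 or more, otherwise 200 mg held | 100 mg |
| 13–16 | up to 400 mg if escalated | 100 mg |

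The durations without valproate are 2 + 2 + 2 + 4 + 2 + 4 = 16 weeks. An administrative stop need not fall on a rating visit, so any week counts. The largest one-step drop is 400 mg daily to zero, or 100 mg daily to zero on valproate.

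**Step 3: number affected and risk.** The documents give no rate for criterion 2 or criterion 7. The count among the planned 200 lamotrigine participants therefore cannot be computed, and it could be zero. The seizure evidence is 2 confounded cases without a denominator, so risk per abrupt stop cannot be computed either.

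**Step 4: taper supply.** The protocol gives no taper steps. Assuming half dose for 7 days and then quarter dose for 7 days:

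- from 100 mg daily: 50 × 7 + 25 × 7 = 525 mg
- from 200 mg daily: 100 × 7 + 50 × 7 = 1,050 mg
- from 300 mg daily: 150 × 7 + 75 × 7 = 1,575 mg
- from 400 mg daily: 200 × 7 + 100 × 7 = 2,100 mg

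**The case against.** The best defence is that the two rules can be read together: a general stop rule, and a specific lamotrigine instruction that qualifies it. Study Medication puts the principal investigator or a co-investigator in charge of dosing and changes. Protection Against Risk promises close follow-up with other treatment recommendations, and Stopping Rules for Efficacy and Safety continues monitoring after study drug stops. A psychiatrist aware of the taper rule would probably apply it.

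These provisions make a mechanical abrupt stop less likely, but they do not change the written instruction. They settle who controls the dose and what happens afterwards, not how lamotrigine is to be stopped. Good judgement should not require departing from the text. Where the protocol wants a taper it says so: the Screening visit section gives prior antidepressants a 1-week taper.

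Two other objections stand in part. Harm is not demonstrated, since the number affected may be nil and the seizure evidence is thin. And a taper may be impossible for some administrative withdrawals: Tracking and Retention drops participants after 3 consecutive missed visits, and someone out of contact may not be reachable.

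A reader might infer from the blanket sentence that all seven triggers break the taper rule. The documents do not support that, because the rule carries its own safety exception and five of the triggers can reasonably fall within it.

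**Conclusion.** The protocol is wrong as written on a narrow point. For an administrative stop with no safety concern, a site cannot follow both the early-discontinuation instruction and the taper rule. For worsening depression alone the conflict is arguable. For the remaining triggers an immediate stop is defensible.

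The size that can be stated is the dose step: up to 400 mg daily to zero in weeks 13 to 16, or 100 mg daily to zero on valproate. This assumes that the participant followed the titration schedule and, for 400 mg, was escalated for persisting symptoms. A reader might also infer a measurable excess of seizures. The documents do not support one, because the 2 cases come from other trials, are confounded and have no denominator.

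The point is worth an amendment because the operational text contradicts the protocol's own drug-safety rule and one sentence removes the contradiction.

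**What to change.** Replace the last sentence of Early discontinuation, item 1, with:

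> Fluoxetine will be discontinued immediately. Lamotrigine will be discontinued immediately when a safety concern warrants it (including criterion 5, any rash not clearly unrelated to the drug, and any other case in which the study physician judges an immediate stop safer, such as active suicidality); otherwise, including administrative stops under criterion 7, it will be tapered over at least 2 weeks.

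Criterion 2 then turns on the physician's judgement. Fluoxetine is unchanged because the documents state no rule against stopping it abruptly. Naming active suicidality matters because the risk section notes that "Overdoses of up to 15 g have been reported, some of which were fatal", so a taper supply should not go to such participants by default. A bare cross-reference to the taper rule would be shorter, but it would leave staff to work out the exception at the moment of stopping.

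The cost is one sentence in an amendment, plus about 2 weeks of drug and follow-up for each lamotrigine participant stopped without a safety concern: 525 mg to 2,100 mg from starting doses of 100 to 400 mg daily, on the assumed steps. The change will not reach participants who have lost contact.
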